1 PROTOCOL SUMMARY

1.1 SYNOPSIS

Title:	Pilot Study of an Optic-to-Audio Device in a Pediatric Cohort with CLN3-related conditions or Low Vision
Study Description:	This is a pilot study of an augmentative visual device, OrCam MyEye 2 (OrCam), in pediatric individuals with CLN3-related conditions or low vision. We hypothesize that, given the relatively simple design and operating procedure of the device, the use of the OrCam by study participants will be safe and feasible. We also hypothesize that the device will enhance their ability to obtain visually based information.
Objectives:	
Primary Assess the safety and feasibility of OrCam use by children with CLN3 or low vision.
 
Secondary Assess the effectiveness of OrCam use by children with CLN3 or low vision.
 
Exploratory Assess the feasibility and effectiveness of OrCam use in CLN3 versus non-CLN3 groups. Optimize methods for assessing efficacy of visual accommodation/assistive devices for the CLN3/NCL population

Endpoints:	
Primary 1) Adverse events during the use of OrCam. 2) Feasibility test. 3) Feasibility questionnaire. 4) Device use diary. The assessment periods will be 1 week at study site and 1 month at home.
 
Secondary 1) Function test of using OrCam. 2) Ability questionnaire.
 
Exploratory 1) Function test. 2) Feasibility, Ability, Applicability questionnaires.

Study Population:	30 individuals age 6-18 years with low vision (20 with CLN3-related conditions, 10 without CLN3) of any gender, demographic, geographic location who meet study eligibility criteria.
Phase:	Not applicable
Description of Sites/Facilities	The NIH Clinical Center will be the only site enrolling participants.
Enrolling Participants:	
Description of Study Intervention:	The study uses the OrCam MyEye 2, a 22.5-g portable, eyeglass-mounted device that converts camera-captured inputs to auditory outputs. Its advertised functions include text reading, facial recognition, and product identification. The study participants and

Abbreviated Title: Pediatric Optic-to-Audio Device Study

[figure not shown]
Version Date: October 25, 2022

parents/guardians will be trained on how to use the device. Evaluations for primary and secondary endpoints will be done following 1 week and 1 month of device use.

Study Duration: 24-36 months.

Participant Duration: 1-2 months

1.2 SCHEMA

Abbreviated Title: Pediatric Optic-to-Audio Device Study
Version Date: March 8, 2022

1.3 SCHEDULE OF ACTIVITIES (SOA)

Procedures	Screening ^{a,d} Up to Day -1	Enrollment Baseline Day 1	Day 2 ^b	Day 3 to 4 ^b	1-Week Evaluations Day 5 ^b	Day 6-11 ^b	Day 12 ^b	Day 13-18 ^b	Day 19 ^b	Day 20-25 ^b	Day 26 ^b	Day 27-32 ^b	1-Month Evaluations Day 33 ^{b,c}
Informed consent ^c	X												
Demographics ^c	X												
Medical history ^c	X												
Physical exam ^d	X												
Vital signs ^d	X												
Ophthalmic evaluation ^d	X												
Neuropsychologic evaluation ^c	X												X ^{d or h}
Audiologic evaluation ^d	X												
UBDRS ^{c,e}	X												
Device training ^{c,f}		X ^d	X ^d	X ^{d or h}	X ^d	X ^h	X ^h	X ^h	X ^h				
Device use ^g			X ^{d or h}	X ^{d or h}		X ^h	X ^h	X ^h	X ^h	X ^h	X ^h		
Adverse events review ^c					X ^{d or h}		X ^h		X ^h		X ^h		X ^{d or h}
Feasibility test ^{c,i}		X ^d			X ^d								X ^{d or h}
Feasibility questionnaire ^{c,j}					X ^{d or h}								X ^{d or h}
Function test ^k		X ^{l, d}			X ^{l, d}								X ^{m, d or h}
Ability questionnaire ⁿ		X ^d			X ^{d or h}								X ^{d or h}
Applicability questionnaire ^o		X ^d											
Quality of Life questionnaires ^p		X ^d											X ^{d or h}
Phlebotomy ^d	X												
Research biospecimen collection ^q	X												

^a Screening evaluations can be done under 18-CH-0002 protocol if participant consented to co-enroll, or under this protocol. Previous evaluations/procedures within stated time frames (**Section 8.1.2**) will be accepted in lieu of repeating.

Abbreviated Title: Pediatric Optic-to-Audio Device Study

Version Date: March 8, 2022

^b +/- 2 days, except for Day 2 to 4 range may be +2 days

^c By in-person or remote technology methods

^d At NIH CC

^e Only in participants with CLN3-related conditions who are not co-enrolled in study 18-CH-0002.

^f **Appendix J** - OrCam MyEye 2 User Guide, Software Version 8.2-EN, Jan 2020.

^g By participant for minimum of 15-30 minutes per day. If participant/parents/guardians encounter issues with device use, they may contact the study team and a video- or audioconference will be scheduled as appropriate.

^h At home

ⁱ **Appendix A.** To be administered by study team to participant

^j **Appendix B.** To be administered by study team to participant if able, and parents/guardians

^k **Appendix C.** To be administered by study team to participants.

^l Full Function Test done with evaluator and participant at NIH CC or partial Function Test done via remote technology (e.g., videoconferencing).

^m Full or partial Function Test if participant cannot return to NIH CC

ⁿ **Appendix D.** To be administered by study team to parents/guardians

^o **Appendix E.** To be administered by study team to parents/guardians

^p **Appendices G - I.** To be administered by study team to participants if appropriate, and parents/guardians

^q If not already done as part of CLN3 natural history protocol (18-CH-0002). Includes at the most: cheek swab (at home or NIH), saliva (at home or NIH), skin biopsy (at NIH), urine (at NIH)

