8.2 EFFICACY ASSESSMENTS

The specific timing of procedures/evaluations to be done at each study visit are captured in **Section 1.3, Schedule of Activities**. Direct evaluations (e.g., Function test) at Screening, Enrollment Baseline Day 1, Device Training Day 2, and 1-Week Evaluations Day 5 visits will be done onsite at the NIH CC. Non-direct evaluations (e.g., surveys and questionnaires) and evaluations on other study days can be done onsite or at home. Non-direct evaluations may be completed using paper or web-based format.

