8.2.1 Clinical Evaluations

1. **Function Test.** The study participants will be asked to complete tasks relating to device-supported daily activities (**Appendix C**). These include identification of printed words (e.g., books, documents, menus, labels, signs) and identification of faces and colors. At Days 1 (baseline) and 5 (1-week evaluation), the Function Test will be done in its entirety via face-to-face encounters. A sub-group of the Function Test items may be done via the use of remote technologies (e.g., videoconferencing). At the 1-month evaluation, if the study participants are able to come to the NIH the Function Test will be done as on Days 1 and 5. If study participants are not able to come for an in-person visit, the sub-group of the Function Test items will be done remotely.
2. **Ability and Applicability Questionnaires.** Parents/Guardians will complete questionnaires of their child's ability to accomplish the tasks in the Function Test without help, and their ratings of how important it would be for their child to accomplish these

tasks without help. (**Appendices D, E**). The questionnaires may be completed using paper or web-based format.

3. **Neuropsychologic Evaluation.** We will assess adaptive behavior using *The Vineland Adaptive Behavior Scales*, Third Edition, Daily Living Scale, based on parent interview. This may be done by methods that do not require in-person meetings (such as via a phone call) to provide adaptability to the protocol and to maximize ability to collect meaningful longitudinal data.
4. **Quality of Life Questionnaires.** Parents/Guardians will complete age-appropriate PedEyeQ[27], PROMIS[28], and Low Vision QOL[29] questionnaires (**Appendices G - I**). The questionnaires may be completed using paper or web-based format.

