9.4.3 Analysis of the Secondary Endpoint(s)

Function Test – Efficacy Scores

Data analysis. Participants' scores will be the sum of items 1 to 7 combining levels a & b and will range from 0 to 14, and the mean duration to complete each task. Analysis will consist of change in scores and mean duration to complete each task from baseline to 1 week and 1 month). No formal statistical tests will be conducted. Interpretation of results will be rule-based.

Rules for data interpretation. Device use is efficacious if at 1-week or 1-month compared to baseline:

- 25% or more of total number of participants increased score by at least 30%
- 25% or more of total number of participants decreased time by at least 30%

Below are some simulations of the power of a paired-sample test for change from baseline, using a sample size of 10 participants. This provides a sense of the possible characteristics of the data and for justifying the sample size.

Simulations for tasks-completed scores

Each simulation study used 1000 replications with $N = 10$. For each replication, baseline and post-baseline sets of scores were randomly generated. Means, standard deviations, and paired-samples t-tests of difference scores (Post-baseline – Baseline)

were computed. Power was computed by the percent of replications (out of 1000) with t-test p-values less than or equal to 0.05. Baselines were generated by randomly selecting, with replication, scores from 0 to 5 with equal probability, 1/6. The baseline range matched the baseline values reported in the adult study. Post-baseline scores included a specified number of baseline cases randomly selected without replacement to improve by 30% (Baseline \times 1.30). Cases with baseline values = 0 were excluded from random selection since percentage change from 0 is undefined.

Simulation 1. Based on the decision rule of 25% of total participants, 3 cases (rounded up since 25% of N= 10 is 2.5) were randomly selected to improve 30% from baseline and the other 7 cases did not improve. *Results: power = proportion of 1000 p-values <= 0.05 = 0.37.*

Simulation 2. 3 cases randomly selected to improve 30% and 7 cases improved by 1 point. *Results: power = proportion of 1000 p-values <= 0.05 = 1.0.*

Simulation 3. 4 cases randomly selected to improve 30% and 6 cases did not improve. *Results: power = proportion of 1000 p-values <= 0.05 = 0.95.*

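### Schedule footnote l allows a partial, remote Function Test on Day 1 and Day 5, against Sections 8.2 and 8.2.1, and Section 9.4.3 has no scoring rule for a partial test at any visit

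*Combined protocol and SAP*

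**What the plan says.** In the Schedule of Activities (Section 1.3), the Function Test cells for Day 1 and Day 5 each carry two markers, l and d. Marker d means at the NIH Clinical Center. Footnote l accepts "Full Function Test done with evaluator and participant at NIH CC or partial Function Test done via remote technology (e.g., videoconferencing". The 1-month cell has a separate footnote, m: "Full or partial Function Test if participant cannot return to NIH CC". Footnote l therefore governs Day 1 and Day 5 only.

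Section 8.2 uses the Function Test as its example of a direct evaluation and says that such evaluations at the "Enrollment Baseline Day 1, Device Training Day 2, and 1-Week Evaluations Day 5 visits will be done onsite at the NIH CC". Section 8.2.1 is more specific: "At Days 1 (baseline) and 5 (1-week evaluation), the Function Test will be done in its entirety via face-to-face encounters". Its next sentence names no visit: "A sub-group of the Function Test items may be done via the use of remote technologies (e.g., videoconferencing". For 1 month it adds: "If study participants are not able to come for an in-person visit, the sub-group of the Function Test items will be done remotely".

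Section 9.4.3 defines the efficacy score: "Participants' scores will be the sum of items 1 to 7 combining levels a & b and will range from 0 to 14". Efficacy is declared if, at 1 week or at 1 month, at least 25% of participants raise their score by at least 30% over baseline. A parallel rule covers a 30% fall in time. Neither 9.4.3 nor the evaluable population in 9.3.2 distinguishes a full test from a partial one.

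**The concern.** Footnote l cannot stand together with marker d, Section 8.2 and Section 8.2.1. The unassigned remote sentence in 8.2.1 leaves that section less than clear as well, so staff could conclude from either place that a partial test is acceptable on Day 1 or Day 5.

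The conflict matters because the score is a raw sum. A test with fewer items has a lower ceiling, and the plan neither prorates nor restricts the comparison to common items. Under Section 4.2 each child's baseline is the control, so a partial Day 1 score would enter both the 1-week and the 1-month comparison. Section 9.2 says the pilot data will inform power calculations for a later efficacy trial, so distorted change scores would carry forward.

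**Working it through.** **Inputs.** From 9.4.3: 7 items at two levels, a 30% per-child threshold and a 25% group threshold. From 9.2: 30 participants. The content of Appendix C is not in the text supplied, so the number of items in the partial test, k of 7, is an assumption shown over a range. Equal performance across items and a non-zero baseline are also assumed.

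**Plan's own figures.** 7 items x 2 levels = 14, which matches the stated range. 25% of 30 = 7.5, so 8 responders are needed; the plan rounds the same way when it takes 25% of 10 as 3. The power simulations in 9.4.3 give 0.37, 0.95 and 0.00 for Simulations 1, 3 and 5. A one-sided paired t-test at 0.05 reproduces these as 0.376, 0.968 and 0.000. They put baseline and follow-up on one scale, so they do not bear on mismatched item sets.

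**Average effect on one child's score.**
- Partial baseline, full follow-up, no true change: apparent change = 7/k - 1.
- Full baseline, partial follow-up, no true change: apparent change = k/7 - 1.
- Full baseline, partial follow-up: true gain needed to register 30% = 1.3 x 7/k - 1.

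| Items in partial test (points) | Partial baseline | Partial follow-up | True gain needed if follow-up is partial |
|---|---|---|---|
| 6 (12) | +17% | -14% | 52% |
| 5 (10) | +40% | -29% | 82% |
| 4 (8) | +75% | -43% | 128% |
| 3 (6) | +133% | -57% | 203% |

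**These are averages.** Take 5 items (10 points), so that the full test adds 4 points.
- A child scoring 2 of 10 needs at least 2.6, that is one more point. At a 20% success rate the chance of gaining none is 0.8^4 = 41%.
- A child scoring 5 of 10 needs at least 6.5, that is two more points. At 50% success the chance of gaining fewer than two is (1 + 4)/16 = 31%.

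**Group rule with no true change.** Simulate 30 children with success rates between 0.1 and 0.5 (assumption), the result on each item held the same at both visits, and some children given a partial baseline. The share of trials in which at least 8 of 30 appear to improve by 30% is:

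| Children with partial baseline | 5 items | 4 items | 3 items |
|---|---|---|---|
| 5 | 0% | 0% | 0% |
| 8 | 1% | 7% | 10% |
| 10 | 9% | 42% | 50% |
| 15 | 63% | 96% | 98% |

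With matched items at both visits the figure is 0%. Fewer than 8 partial baselines cannot meet the rule alone, because matched children contribute no responders.

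**Group rule with a true gain of at least 30% in every child.** If 10 or 20 of 30 have a partial follow-up, the rule is still met in about 100% of trials. If all 30 do, it is met in 6% (5 items), 0.1% (4 items) and 0% (3 items).

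**Time criterion.** This is a mean duration per task, so a partial test affects it through which items are included rather than through their number.

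**The case against.** The strongest reply is that footnote l is a stray clause that the rest of the plan overrides. Much supports this. Marker d is in the same cells. The Schedule writes d or h where it intends home testing, as at 1 month. The Feasibility test row carries marker c (in person or remote), and the Function Test row does not. Sections 8.2 and 8.2.1 agree with each other, exclusion criterion 3 removes children medically unable to travel for in-person parts, and the compensation table in 5.7.2 has a remote column only for 1 month. It stands that full, on-site testing is the evident intention and that harm arises only if staff act on the footnote. It does not remove the conflict, and the scoring gap in 9.4.3 remains either way.

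Appendix C might also define the remote items and their scoring. That cannot be checked from the text supplied, so nothing here rests on its being silent.

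A reader might infer three stronger things, none of which the documents support.
- **That a partial baseline is beyond repair.** It is not: the later test can be scored on the items given on Day 1. Only the full 0-14 endpoint is lost.
- **That with 5 or fewer items every such child becomes a responder, so a handful would largely satisfy the rule.** The ratio is an average, and the worked cases show 31% to 41% of such children not crossing 30%.
- **That the plan is tilted towards efficacy.** The direction depends on which visit is partial, and the same partial set at both visits causes no mismatch.

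**Conclusion.** The inconsistency is real and should be corrected, but it is limited in reach. It concerns a secondary, rule-based endpoint of a pilot study with no formal test. A few mismatched children change their own responder status. With no true effect, about 10 of 30 partial baselines are needed before the 8-of-30 rule is at real risk; fewer could matter if genuine responders already lie near the threshold. These sizes rest on the assumed number of items, equal performance across items and, for the group figures, the assumed success rates.

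The firmer instance is at 1 month, where 8.2.1 and footnote m expressly allow a partial test against a full baseline. There the mismatch tends to hide improvement. It would overturn the 1-month result only if nearly all children were tested remotely, and a sound 1-week result could still satisfy the rule.

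**What to change.** 1. In footnote l, delete the alternative of a partial test by remote technology. In 8.2.1, limit the sentence on a remote sub-group of items to the 1-month visit. Day 1 and Day 5 are then full and on site wherever the plan mentions them.
2. Add to 9.4.3: whenever a Function Test at any visit is partial, change from baseline in score and in time is computed only on the items given at both visits, and not against the full 0-14 sum.

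The cost is two small wording changes and one added sentence. No visit is added, since 8.2 already requires attendance on Day 1 and Day 5. The downside is that change scores for children with a partial test rest on fewer items and are less precise.

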2 INTRODUCTION

2.1 STUDY RATIONALE

CLN3 is a fatal, lysosomal disease that results in progressive neurodegeneration. It is the most common type of the 13 disorders of neuronal ceroid lipofuscinosis with incidence estimates ranging from 1/12,500 to 1/100,000 in European and USA populations. The initial clinical presentation is vision loss, resulting in legal blindness by 7-8 years of age in most individuals with classic CLN3 disease. Cognitive impairment and behavioral dysfunctions are also early presenting symptoms, followed by seizures and motor dysfunction. Current life-expectancy for affected individuals is in to the second to third decade of life.

The early and relatively rapid visual changes significantly impact the quality of life of individuals with CLN3. Current standard accommodative approaches for the progressive blindness, i.e., enlarged fonts, Braille, sign language, have limited applicability given the multiple disabilities associated with the neurodegeneration. Though treatment trials are in development, none specifically targets low vision. Thus, approaches to provide means for obtaining vision-related inputs are needed. Additionally, better understanding of parental goals for their child in terms of ability to perform vision-related tasks will inform the development of future accommodations. To begin addressing these knowledge gaps, this protocol will assess the safety, feasibility, and efficacy of the use of an augmentative visual device in a cohort of children and adolescents with CLN3, low vision, and intellectual disability. This protocol will further explore parental objectives for their child's function, and the potential of the device in addressing these.

Information on the use of the OrCam MyEye 2 device in the pediatric population with low vision is not available. Thus, to evaluate the feasibility and effectiveness of this device in children with low vision, and no concomitant neurodegenerative process, we will include a cohort of pediatric individuals with low vision but without a CLN3-related disorder.

2.2 BACKGROUND

CLN3 (JNCL, Batten Disease, MIM 204300) is an autosomal recessive, fatal, lysosomal disease that results in progressive neurodegeneration.[\[1-3\]](#) It is one of 13 disorders categorized as neuronal ceroid lipofuscinosis. In aggregate, these are considered the most common neurodegenerative disorders in children, with incidence estimates ranging from 1/12,500 to 1/100,000 in European and USA populations.[\[2, 4\]](#)

The disease presentation typically involves vision loss observed around pre-school years, with eventual progression to blindness within 1-3 years.[\[5-7\]](#) The underlying pathophysiology involves intracellular accumulation of ceroid lipofuscin materials in retinal ganglions, and possibly in photoreceptors.[\[8-10\]](#) This manifests on ophthalmic measures as decreased electrical responses to stimuli on electroretinogram [\[5, 7, 11\]](#) and thinning of the retinal cell layers on pathology and optical coherence tomography [\[7, 9, 12\]](#). Neurocognitive development plateaus around 7-10 years of age and progresses to dementia starting in the early teen years.[\[13-15\]](#) Behavioral, psychiatric, seizure, and motor disorders are also common findings in individuals with CLN3.[\[1, 16\]](#) Current estimated average life expectancy is in the 20-30's.[\[2\]](#) There are no therapies for this devastating disorder. Therapeutic trials using gene therapy or small molecules are in the early stages of implementation.[\[17\]](#) Pathogenic variants in *CLN3* have also been associated with a non-syndromic phenotype that appears to affect vision only.[\[18, 1\]](#)

Abbreviated Title: Pediatric Optic-to-Audio Device Study

Version Date: March 8, 2022

[figure not shown]

Figure 1. Visual ability of CLN3 natural history study participants (n=22).

the range of intellectual disability (≤ -2 SD; **Figure 2, left panel**), with daily living skill scores also significantly below the mean standard score (**Figure 2, right panel**).

The loss of a major means of sensory input likely contributes to some of the behavior dysfunctions such as anxiety and perseveration in children with CLN3.[\[20\]](#) Quality of life for the affected child and family members is profoundly impacted as they adapt to the blindness and disease.[\[20, 21\]](#) When asked to rank in order (1=most desirable) the symptoms they would like to see being addressed by future interventions, 37% of mothers (n=19) and 47% of fathers (n=15) in the Natural History study cohort chose vision as number one.

[figure not shown]

Figure 2. Adaptive behavior of CLN3 natural history study participants as measured by Vineland-3 parental interview (n=22). Left panel: Adaptive behavior composite standardized scores. Right panel: Daily Living Skill standardized sub-scores. Mean score = 100. Standard deviation (SD) = 15.

Current approaches towards therapeutic intervention for CLN3 appropriately focus on addressing neurologic or systemic symptoms.[\[22-24\]](#) However, these approaches have unclear impact on visual ability as information on the effectiveness of blood-retinal barrier delivery has not been published. While many of the study participants were initially started on Braille, the

To augment the development of biomarker discovery for application in diagnosis and therapeutic trial monitoring, we initiated a Natural History study of individuals with CLN3 (NCT03307304). The study includes extensive evaluations including ophthalmologic, neurodevelopmental, audiologic, functional visual and occupational therapy measures. Of the initial 22 study participants enrolled, all but two have vision qualifying for legal blindness status (**Figure 1**). Vineland-3 adaptive behavior composite (ABC) assessment, a parental report measure of an individual's real-world functioning with good correlation with standard IQ testing, showed that a significant number of the study participants older than 8 years of age scored in

concomitant intellectual disability limited them from attaining the skill level necessary for efficient use. Other alternative and augmentative modes for communication and sensory inputs such as auditory (e.g. books on tape) and tactile (e.g. textured objects) may be more applicable[21]. Study participants in the NICHD natural history cohort have preserved hearing ability and are reported by parents to maintain interests in listening to stories or movies on their electronic devices. The OrCam MyEye 2[25] is a portable, optic-to-audio assistive vision device that contains features likely applicable to the CLN3 cohort. The eyeglass-mounted device (**Figure 3**) is advertised to allow users to read text, and to identify faces, objects and colors by pointing and aiming the camera at the intended target[25]. A pilot study

Figure 3. OrCam MyEye 2.
<https://www.orcam.com/en/blog/category/general/>, on 3/8/2020.

using the OrCam in 12 adults with low vision and intact cognition showed improved ability in reading and daily function tasks[26]. The adult study participants also found the OrCam to be easy to use and would recommend it to others with low vision. No study in children or in individuals with CLN3 is available.

